number	• Newborns whose parents want to sign the information form – informed consent.	
	Consent	
	Exclusion criteria	
	• Informed consent is not signed	
	 Infants of birth weight ≥ 1.500 gramms and/or gestational age > 32 weeks infants hospitalized after 36 hours of life 	
	Infants with ophthalmologic disease at randomization	
	• infants with severe malformations	
	Number of nationts about to be varietaved	
	Number of patients about to be registered It is expected to register a total number of 50 newborns divided in two groups:	
	• Experimental group A: 25 newborns treated;	
	Control group B: 25 newborns treated.	
Randomization	Subsequently enrollment patients will be randomly divided into Group A and Group B throught a web system that allows the randomization into three different recruitment centers	

	T
Number of centres	Multicenter pilot study. At the study will participate three Italian experimental centres: Naples, Siena and
	Padova.
	The centre from Naples will be the national coordinator and the center from Siena
	will handle in a centralized way the laboratory results. The center from Padova
	will help to recruit an adequate number of cases.
Sample size	BAP and TH are two bio-markers with different hypothetical changes clearly different. For this reason we will use the study method proceeds by the following online site http://clincalc.com/stats/samplesize.aspx (Rosner B. Fundamentals of Biostatistics. 7th ed. Boston, MA: Brooks/Cole; 2011). The inserted reference values are for BAP 2361 (\pm 466) μ mol/L and for TH 156.75 (\pm 64.0) Ucarr (Perrone S., Longini M. et. Al). The difference for BAP that we hypothesize to find is an increase of at least 500 μ mol / L which is approximately 20% of the control data. By setting α = 0.05% and β =0.1% with a power of 90% the number of samples required is 25 + 25 = 50. For the TH assume a decrease of 50 Ucarr which is approximately 30% of the
	data of the control. By setting $\alpha = 0.05\%$ and $\beta = 0.2\%$ with a power of '80% also in this case the required number of samples is $25 + 25 = 50$.
	However $25 + 25$ is the minimum number. Taking into account any ongoing study waivers (parents may request to discontinue treatment at any time) which go beyond statistical calculations. So in case of necessity we will recruit a number of infants to reach the minimum number according to the design of the protocol (25 $+$ 25).
Treatment and	Products administered:

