laboratory investigations foreseen. The second semester will be used to study and analyse the results achieved.

Procedures

Methodology:

When born, premature newborns that are comply with the inclusion parameters will be introduced and separated in two random groups (A and B).

All newborns, during the observation period, will be submitted to the blood collection (1 ml) from the umbilical cord and peripheral (at the same time with the routine collections) on which there will be performed blood gas analysis and oxidative stress markers (TH and BAP). All registered newborns will also be submitted to the verification of their history concerning the examination and collection, in view of evaluation the presence or absence of ROP, NEC, IVH, BPD and infections.

Collection Time

- T0, basic at birth, before begining the treatment: blood collection from the umbilical vein.
- T1, first check, to 15 days after initiation of treatment: peripheral blood collection in view of verifying it before the Lutein/zeaxanthin administration.
- T2, second check, at 30th day since the begining of treatment: peripheral blood collection in view of verifying it before the Lutein/zeaxanthin administration.

The parents will be informed concerning the experimental procedure and the checks schedules.

It will be required the written consent of the parents.

The protocol shall be submitted to approval to the local ethics commission.

Evaluation Parameters:

Efficiency:

a) Evaluation of oxidative stress biomarkers in the peripheral blood of the premature newborn before and after the treatment.

Tolerability:

There will be transcribed on the data sheet possible adverse events which may be observed by the doctor.

Evaluation Scale

- a) Evaluation of the oxidative stress: by deremining the oxidative stress biomarkers and registering them in the data sheet.
- b) They must be indicated:

Demographic Characteristics

- Sex
- Gestational Age
- Weight (with percentile)
- Mode of delivery
- Preeclampsia
- Premature rupture of membranes
- Using steroids before birth
- Using antibiotics before birth
- Use of drugs or harmful substance before birth

Clinical features

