	 Apgar score Use of surfactant Umbilical catheter CVC location and duration Intubation Mechanical ventilation (procedures and time) Supplementation of O2 Incidence of infections Use and type of antibiotics Use and type of antifungal Use and type of post-natal steroids Use and type inotropic Use of NPT Duration of treatment in NICU Nutritional Characteristics: Oral feeding start time Exclusive oral feeding start time Fluid volume Intake calories (protein, carbohydrates and fats) Use of maternal and /or uman milk Other therapies associated and/or permitted During the trial period it is not permitted any product administration or antioxidant activities (anti-radicals) or products which contain even a sole
Basic examination	component having this result, excepting the protocol. At birth, as it is foreseen by newborn protocols, the babies will be submitted to
	several medical examinations.
Control examination	From the Birthing Unit, the newborns will be transered to intensive care rooms where they will be submitted to multiple control examinations.
Follow-up examinations	As it is foreseen in neonatal protocols.
Statistical Analysis	The Student t test for independent data is the type of analysis that will be used to assess statistically significant differences between the parameters recorded in the two groups (treated and control). The Student t test is the method of choice for analysis as it allows to evaluate the values of a continuous random variable measured in not very many samples (25 subjects per group). It will be using the statistical package SPSS system.

REFERENCES

Lutein: description, pharmacokinetics activity and characteristics, mechanism of action, safety and tolerability

- 1. Shao, A. and Hathcock, JN. Risk assessment for the carotenoids lutein and lycopene. Regul Toxicol Pharmacol. 2006 Aug;45(3):289-98.
- 3. Khachik F, de Moura FF, Chew EY, Douglass LW, Ferris FL 3rd, Kim J, Thompson DJ. The effect of lutein and zeaxanthin supplementation on metabolites of these carotenoids in the serum of persons aged 60 or older. Invest Ophthalmol Vis Sci. 2006 Dec;47(12):5234-42.

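### The only planned test uses neither centre nor gestational age; whether its standard error is right depends on an allocation scheme the plan does not state, and TH has no power to spare

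*Combined protocol and SAP*

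**What the plan says.** The Statistical Analysis section of the combined protocol and SAP gives one method for comparing treated and control infants: "The Student t test for independent data is the type of analysis that will be used". It names no covariate, stratum or adjusted model.

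The Number of centres section says "At the study will participate three Italian experimental centres". It adds that one of them, Siena, "will handle in a centralized way the laboratory results". The Randomization section says infants are divided between the groups "throught a web system that allows the randomization into three different recruitment centers". It does not mention stratification, blocks or a separate list per centre, and the Procedures section speaks only of two random groups. Also under Procedures, "Gestational Age" is listed among the demographic characteristics to be recorded.

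For TH, the Sample size section assumes a fall of 50 Ucarr with SD 64.0 and states 80% power with 25 + 25 infants.

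**The concern.** Two questions arise.

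The first is validity. If the web system balances the arms within each centre, the design removes between-centre variation from the treatment difference. A t test that ignores centre still counts that variation in its standard error. The interval is then too wide and the test rejects too rarely under the null.

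The second is precision. Entry is at 32 weeks or less and/or 1,500 g or less, with no lower limit, so maturity can vary widely. The protocol's introduction names oxygen exposure, phototherapy and delivery-room practice as sources of free radicals. It is a reasonable inference, not a statement in the plan, that these differ by hospital and by maturity. If centre and gestational age predict TH or BAP, a test that ignores them gives up precision that data already being collected could supply. The loss would matter most for TH, where the sample size leaves no margin.

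**Working it through.** **Inputs from the Sample size section.** TH: difference 50, SD 64.0. BAP: difference 500, SD 466. 25 per arm. Alpha is printed as 0.05% and is read here as 5%, two-sided, because the TH sample size reproduces only on that reading.

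**Assumptions, not in the documents.** The share of variance explained by centre and gestational age (R²) is shown from 0 to 30%. Simulations use centre sizes of 20, 16 and 14.

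**Step 1: the plan's TH figure.** n per arm = 2 × [64 × (1.960 + 0.842) / 50]² = 25.7, so 26 against the stated 25. The TH calculation reproduces to within one infant per arm.

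**Step 2: power of the planned t test.** The standard error is 64 × √(2/25) = 18.10, and the noncentrality is 50 / 18.10 = 2.76.
- TH: normal approximation Φ(2.76 − 1.96) = 78.9%; exact noncentral t with 48 df, 77.2%.
- BAP: noncentrality 500 / (466 × √(2/25)) = 3.79; exact power 96%.

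**Step 3: type I error of the t test if allocation is balanced within centre.** The estimate's true standard error is √(1 − R²) times the one the t test uses, where R² is the share due to centre. The true error rate is therefore about 2 × P(T > 2.011 / √(1 − R²)) with 48 df.
- Centre R² 10%: threshold 2.119, error 3.9%
- 20%: threshold 2.248, error 2.9%
- 30%: threshold 2.403, error 2.0%

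Simulation agrees to about half a point. Without within-centre balance, simulation puts the t test at about 5% in every scenario. For example, with centre at 10%, the mean estimated standard error was about 18.1 and the true one about 18.0.

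**Step 4: TH power after adjustment for centre and gestational age.** The residual SD is 64 × √(1 − R²), and three extra parameters leave 45 df. The variance also needs an allowance for chance imbalance in the covariates, of 1 + k/44. Here k = 1 if centre is balanced by design (only gestational age can be unbalanced), and k = 3 if it is not.

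| Total R² | Residual SD | Adjusted power, balanced within centre | Adjusted power, not balanced |
|---|---|---|---|
| 0 | 64.0 | 76% | 74% |
| 10% | 60.7 | 80–81% | 79% |
| 20% | 57.2 | 84–85% | 83% |
| 30% | 53.5 | 89–90% | 88% |

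Ranges show the spread between formula and simulation. The unadjusted comparator is about 77% without balance. With balance it is 77 to 81%, rising with the share due to centre.

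**Step 5: break-even.** Without the imbalance allowance, an R² of 7% appears enough to reach 80%. With it, an R² of 7% gives about 79% under within-centre balance and 77% without. Reaching 80% takes about 10% with balance and about 13% without.

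**Step 6: interval width.** The unadjusted 95% half-width is 2.011 × 18.10 = 36.4 Ucarr. Adjusted, without within-centre balance, it is 37.7, 35.7, 33.7 and 31.5 at R² of 0, 10, 20 and 30%.

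**The case against.** The strongest objection is that nothing here invalidates the planned test. A reader might infer that the error bars are too wide as a matter of fact. The documents do not support that: the bias needs allocation balanced within centre on a prognostic factor, and a web system reaching three centres fits a single central list just as well. Without such balance the t test holds its 5% level. Even with it, the error is conservative, and the estimate stays unbiased under randomisation. Chance imbalance in gestational age is already covered by a valid standard error.

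A reader might also infer that TH power is certainly being left unused. No passage relates TH or BAP to centre or gestational age, so every R² above is assumed. Central handling of laboratory results limits one route to centre differences, though not differences in care or in how samples are collected and transported. BAP gains little. Adjustment is not free either: with useless covariates it costs 1 to 3 points of TH power.

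Finally, this is a 50-infant pilot, and the plan justifies a simple test by the small sample.

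All of this stands, and it makes the point an improvement in efficiency rather than the repair of an invalid analysis. It does not remove the need to state the allocation scheme, because the appropriate standard error depends on it. Nor does it offset the asymmetry for TH: a loss of at most about 3 points against a gain of about 6 points or more at an R² of 20% without balance.

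**Conclusion.** The point holds conditionally. It is certain that the only planned test omits centre and gestational age, that the allocation scheme is not described well enough to tell whether this biases the standard error, and that TH starts at about 77% exact power rather than 80%.

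It is conditional that the t test is conservative, which requires within-centre balance and a prognostic centre. It is also conditional that adjustment adds power. At an R² of 10% the gain is small, about 2 points under either scheme. At 20 to 30% it is clear under either scheme: roughly 6 to 11 points without balance, and about 5 to 9 with balance if the explained variance is all due to centre. These sizes rest on two-sided 5%, the plan's own TH difference and SD, 25 evaluable infants per arm and the assumed R².

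**What to change.** **Randomization section.** State whether the web system allocates 1:1 in blocks within centre.

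**Statistical Analysis section.** Pre-specify, for TH and BAP, a linear model with treatment group and continuous gestational age, plus any baseline marker term the sponsor adopts. Include centre if allocation is balanced within centre. Report the adjusted difference with its 95% confidence interval, and keep the independent t test as a sensitivity analysis. Fix the covariates before the code is broken, so that they cannot be chosen on the results.

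**Cost.** A few sentences and one general linear model in SPSS, the package already named. No extra infants or measurements are needed. The statistical price is up to 3 degrees of freedom and, if the covariates explain nothing, about 1 point of TH power. That rises to about 3 points if centre is fitted although allocation was not balanced on it.

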Because the polyunsaturated fat acids are very sensitive to oxidation, the modification of their plasmatic levels influences the state of the antioxidant systems on the mother and subsequently to the fetus. Many studies have proved that the increase of the susceptibility to the peroxidation of polyunsatured fat acids on pregnant women is accompanied by an equivalent increase of the tocopherol plasmatic concentrations which, immediately after birth, decrease sharply.

The plasmatic concentrations of antioxidants on newborns, comparative to the mother's were smaller. In the umbilical cord, the levels of tocopherols and carotenoids are significantly smaller that the ones registered in the maternal plasma and the concentration of polyunsaturated fat acids on the newborn is significantly higher and a lot more increased than on the mother.

Furthermore, specific studies showed a growing interest towords the oxidative stress and oxygen reactive species which supposedly accumulate after birth. Many practices usualy used in the delivery room, for example the drugs given to pregnant woman to ease her pain, the newborn's extraction methods, the techniques to minimize body temperature decrease, blocking the umbilical cord and especially the use of oxygen to 100 % or a ventilated room (Room Air, RA) for newborns presenting asphyxia signs, do not always prove to be efficient, but they can also compromise the health of the newborn as a result of a significant increase of free radicals.

Some specific studies have compared the levels of free radicals, highlighted with particular markers, in the plasma of the umbilical cord of newborns with asphyxia treated 100% with oxygen or 21% with oxygen, comparative to a control group of children without asphyxia. The levels of free radicals were significantly increased immediately after birth in all three groups and grew at the two groups of newborns with asphyxia. In the group treated 21% with oxygen, these values decreased and at 28 days after birth, they have reached the same level of the newborns without asphyxia, whereas at the group treated 100% with oxygen the levels of free radicals still remains very high.

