Thus, it results that a short exposure of the newborn to 100% oxygen is the cause of an extended oxidative stress state and a consistent increase of free radicals which seem to be involved in different diseases and pathologies during the first months of life, especially in the preterm infant increasing the incidence of ROP, IVH, BPD, NEC and infections significantly.

As a result, it is desirable that the newborn can increase the level of antioxidant protection to reestablish the oxido-reductive balance and to prevent the problems occurred from an extended exposure to high levels of free radicals and oxygen reactive species.

Oxidative stress, as well as in the case of age diseases, is considered one of the main factors which determine the deterioration of the retina. The attempt to maintain a correct balance between oxidant and antioxidant factors can help to prevent or reduce damage to the eyes or other tissues that occur in the newborn, especially preterm.

The premature birth is the most frequent cause of mortality, morbidity and disability. Premature babies have an extremly high risk to develop ocular or neurological lesions. The main complication at visual level that may appear is called retinopathy of prematurity, so called ROP. Oxidative stress is involved in

the etiology of this disease. In fact, premature babies, because of repiratory issues, are oftenly exposed to potentially damaging oxygen concentrations or to phototherapy with high blue light intensity. These therapuetical practices are sources of free radicals.

The lutein and zeaxanthin present in the macular pigment, due to their capacity to absorb blue light and their antioxidant action, could have an important role in protecting the eyes of the newborn against damages produced by intense light.

On adults, different elements suggest a protective action of lutein against photooxidative damage, proved by numerous studies.

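### The unadjusted t test leaves early high-concentration oxygen, gestational age and the T0 value in the error term; it is valid but loses precision, mainly for TH

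*Combined protocol and SAP*

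**What the plan says.** The Statistical Analysis section gives a single method for comparing treated and control infants: "The Student t test for independent data is the type of analysis that will be used to assess statistically significant differences". It names no covariate, no baseline adjustment and no time point. The Randomization section describes a web system across three centres and states no prognostic stratification factor.

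The background describes studies of newborns with asphyxia resuscitated with 21% or 100% oxygen. In the 21% group, "at 28 days after birth, they have reached the same level of the newborns without asphyxia"; by contrast, "at the group treated 100% with oxygen the levels of free radicals still remains very high". The protocol concludes that "a short exposure of the newborn to 100% oxygen is the cause of an extended oxidative stress state", and later says that premature babies "are oftenly exposed to potentially damaging oxygen concentrations".

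Under Procedures, Collection Time, the baseline sample is "T0, basic at birth, before begining the treatment: blood collection from the umbilical vein". T2 is peripheral blood on the 30th day of treatment, and treatment starts within 36 hours of life. T2 therefore falls at about day 30 to 31 of life, close to the 28 days cited in the background.

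The data sheet (Evaluation Scale) lists gestational age among the demographic characteristics, and Apgar score, intubation and "Supplementation of O2" among the clinical features. None of these is given a role in the analysis. The oxygen item does not separate oxygen before the first dose from oxygen given later.

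**The concern.** The protocol names a cause of raised free radicals that lasts to about the time of its last measurement, and says its own population often meets that kind of exposure. The analysis then treats the resulting variation as noise.

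With 25 infants per arm, a predictor left in the error term widens the confidence interval. If the arms happen to differ in exposure, the unadjusted difference carries that imbalance, and the planned analysis has nothing to separate it from the treatment effect. TH is the marker at risk, because its sample size has no slack.

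Adjusting for T0 alone would not close the gap. Cord blood taken at birth cannot reflect oxygen that the infant receives afterwards. The timing is in the protocol; the consequence is an inference from it.

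**Working it through.** **Inputs from the Sample size section.** TH: difference 50 Ucarr, SD 64.0, 80% power. BAP: difference 500 µmol/L, SD 466, 90% power. Both give 25 per arm. Alpha is printed as 0.05% and read here as 0.05. Sidedness is not stated, so two-sided is assumed.

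**Step 1. The plan's own figures.** The standard error of a difference in means is SD × √(2/25).

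- TH: 64 × √0.08 = 18.1 Ucarr. The noncentrality is 50/18.1 = 2.76, and with 48 df the noncentral t gives 77.2% power (normal approximation 78.9%). For 80% power, 26 per arm are needed (27 with the t distribution), so the stated 25 reproduces closely but without margin.
- BAP: 466 × √0.08 = 131.8 µmol/L. The noncentrality is 500/131.8 = 3.79, and the power is 96%. At the stated 90%, 19 to 20 per arm would do. The mismatch is on the safe side and nothing here depends on it.

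**Step 2. What adjustment could gain for TH.** The documents give neither the share of infants highly exposed (p) nor the shift in TH that exposure causes (δ, in residual SD units). Both are assumed: p from 10% to 50%, δ from 0.5 to 1.5. SD 64 is taken as the total SD, so exposure explains

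R² = p(1−p)δ² / [1 + p(1−p)δ²],

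and the residual SD is 64 × √(1−R²). Power uses 50 − 2 − 3 = 45 df, for a model with three covariates. T0 and gestational age are credited with no explanatory power, because the documents give no correlation for them.

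| p | δ | R² | Residual SD | TH power |
|---|---|---|---|---|
| 10% | 0.5 | 2% | 63.3 | 78% |
| 10% | 1.0 | 8% | 61.3 | 81% |
| 10% | 1.5 | 17% | 58.4 | 84% |
| 30% | 0.5 | 5% | 62.4 | 79% |
| 30% | 1.0 | 17% | 58.2 | 84% |
| 30% | 1.5 | 32% | 52.7 | 91% |
| 50% | 0.5 | 6% | 62.1 | 80% |
| 50% | 1.0 | 20% | 57.2 | 86% |
| 50% | 1.5 | 36% | 51.2 | 92% |

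The comparison is 77% unadjusted. BAP starts at 96%, so it can gain at most 4 points.

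**Step 3. If the exposure adds variance beyond SD 64.** The reference values come from an earlier study, and the background describes that group's previous work as done in term infants. SD 64 may therefore not contain the oxygen variation of a preterm population. Then total SD = 64 × √(1 + p(1−p)δ²). At p = 30% and δ = 0.5 to 1.5, this is 66 to 78 Ucarr. Unadjusted TH power falls to between 75% and 61%, and adjustment restores about 77%.

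**Step 4. Chance imbalance.** Treat the exposed counts as two independent Binomial(25, p) variables. The probability that the arms differ by 5 or more infants is 3%, 11%, 16% and 20% at p = 10%, 20%, 30% and 50%. A difference of exactly 5 is 5/25 = 0.2. At p = 30% it moves the TH difference by 0.2 × δ × residual SD: 0.2 × 0.5 × 62.4 = 6 Ucarr, 0.2 × 1.0 × 58.2 = 12 Ucarr, or 0.2 × 1.5 × 52.7 = 16 Ucarr. That is 12% to 32% of the hypothesised 50.

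**The case against.** The strongest reply is that a t test is a sound choice for a 50-infant randomised pilot. It keeps its type I error and is unbiased on average. The imbalance in step 4 is not an extra error: when SD 64 is the total SD, exposure variance is already in the 18.1 Ucarr standard error, and a shift of 6 to 16 Ucarr is less than one such standard error and can go either way. This stands. A reader might infer that the planned analysis is biased or invalid; the documents do not support that.

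A reader might also take the background to say that any oxygen at birth keeps free radicals high for a month. It says so only for asphyxiated newborns given 100%; the 21% group normalised. It gives no 28-day data for preterm infants and no count of how many enrolled infants will be exposed. This stands too, and it is why the size is left open. At 10% exposed and a 0.5 SD shift, the gain is about one point.

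Third, the background passages concern free radicals, not antioxidant potential, and BAP has power to spare. The precision argument therefore does not carry over to BAP.

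Finally, T0 should not be dismissed. Cord blood may partly reflect perinatal asphyxia, the condition for which the oxygen was given in the cited studies. It is the same marker's own baseline and belongs in the model, but it cannot carry exposure that comes after it was drawn.

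**Conclusion.** The point holds as one of efficiency and conditional balance, mainly for TH. The protocol identifies a lasting influence on its outcome, has a field for recording it, and leaves it out of the analysis together with gestational age and T0. TH has 77% power on the plan's inputs, below the 80% stated, so recoverable precision is worth having.

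How much is recoverable cannot be read from the documents. Under the assumed exposure shares and shifts, adjusted TH power is 78% to 92%, so the gain runs from about 1 to 15 points. If preterm oxygen exposure adds variance beyond SD 64, adjustment would instead mainly protect the power already claimed. All of this assumes a two-sided 5% test and 25 evaluable infants per arm.

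The change is worth making before unblinding because it is cheap. An undivided oxygen field may not be separable later, and covariates chosen after seeing the data would not be credible.

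**What to change.** In the Statistical Analysis section, make the main analysis of TH at T2 a pre-specified linear model of the T2 value on:

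- arm;
- the T0 value of the same marker;
- gestational age;
- oxygen exposure before the first dose, either as the highest concentration received or as high versus none/low with the cut-off fixed before unblinding.

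Use the same model for BAP for consistency, analyse T1 in the same way as secondary, and keep the t test as a supportive result.

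On the data sheet, split the oxygen item into before and after the first dose, and use only the pre-dose part. Treatment cannot have affected oxygen given before it began. Later oxygen may be affected by treatment and should not be a covariate.

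The cost is a few sentences, three error degrees of freedom (48 to 45), one split field and one exposure definition to settle in advance. A high/low split also discards some information, which favours the recorded concentration if it is available. No extra infants or procedures are needed.

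### TH and BAP are measured at day 15 and day 30 on the same infant, but the planned independent-data t test leaves an infant without day 30 out of that comparison and does not use the infant's day-15 value to inform it

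*Combined protocol and SAP*

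**What the plan says.** Under Procedures (Collection Time), each infant has one cord sample, "T0, basic at birth, before begining the treatment: blood collection from the umbilical vein", and two peripheral samples after treatment starts: "T1, first check, to 15 days after initiation of treatment" and "T2, second check, at 30th day since the begining of treatment". The Methodology text adds that blood is taken "at the same time with the routine collections".

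The Statistical Analysis section gives one method: "The Student t test for independent data is the type of analysis that will be used". It compares treated with control infants on whatever was recorded, in SPSS. It does not name a visit, a summary over visits, a longitudinal model, an analysis set or a rule for missing samples.

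Losses are mentioned only under Sample size. It notes that "parents may request to discontinue treatment at any time", places such withdrawals outside the calculation, and says that more infants will be recruited if needed to reach 25 + 25. It does not say whether an infant lost after T1 counts towards the 25. The background text gives a general reason to expect incomplete follow-up: "The premature birth is the most frequent cause of mortality, morbidity and disability".

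**The concern.** T1 and T2 values from one infant are likely to be correlated, so T1 carries information about a T2 value that was never obtained. A t test on T2 ignores it and compares only the infants who reached day 30 with a sample.

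That matters most if loss is selective. Suppose infants with high TH at T1 are more likely to have no T2, and the product has already lowered TH by T1. More high-TH infants then vanish from the control arm than from the treated arm, and the day-30 difference shrinks towards zero. TH has little room for this, because it was sized at 80% power. Replacement infants pass through the same filter, so they add numbers without removing the selection.

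This is separate from how the cord sample at T0 should be used.

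**Working it through.** **1. The plan's own TH figure.** Inputs from Sample size: SD 64.0, difference 50, power 80%. The printed α of 0.05% is read as 0.05, assumed two-sided.

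n per arm = 2(1.960 + 0.842)² × 64² / 50² = 2 × 7.85 × 1.638 = 25.7, so 26 against the stated 25. With 25 per arm and complete data, power is 78.9% (normal approximation) or 77.2% (t distribution).

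**2. Assumptions that the documents do not supply.** T2 is missing in 50% of infants with T1 TH above 180 and in 5% of the rest. The effect is 50 at both visits. The T1–T2 correlation ρ is 0.5 to 0.7. Values are normal, with control mean 156.75 and SD 64.

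**3. Bias of the T2 t test.** Write c for the cut-off in SD units and φ for the normal density.
- Control: c = (180 − 156.75)/64 = 0.363; P(T1 > 180) = 0.358; loss = 0.05 + 0.45 × 0.358 = 21.1%.
- Treated: mean 106.75; c = 73.25/64 = 1.145; P(T1 > 180) = 0.126; loss = 0.05 + 0.45 × 0.126 = 10.7%.
- Overall loss is about 16%.

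Among infants who keep a T2, the T1 mean is lower than it should be by 64 × 0.45 φ(c) / (1 − loss):
- Control: 64 × 0.45 × 0.3735 / 0.789 = 13.64.
- Treated: 64 × 0.45 × 0.2072 / 0.893 = 6.68.

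The difference, 6.96, carries over to T2 in proportion to ρ:
- ρ = 0.5: 50 − 3.5 = 46.5.
- ρ = 0.7: 50 − 4.9 = 45.1.

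Nothing here depends on the number recruited, so top-up leaves the bias as it is. A joint model adds back, in each arm, the slope times (T1 mean of all infants − T1 mean of those with T2). That restores 50.

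**4. Power under the same assumptions, by simulation.** The test is two-sided at 5%. The joint analysis is the maximum-likelihood estimator for T1 complete and T2 partly missing. Top-up means recruiting until each arm has 25 T2 values.

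| | t test: estimate | t test: power | joint model: estimate | joint model: power |
|---|---|---|---|---|
| 25 per arm, no top-up | 46.4 (ρ 0.5), 45.6 (ρ 0.7) | 64–65% | about 50 | 70–73% |
| topped up to 25 T2 values per arm | 46.6 (ρ 0.5), 44.9 (ρ 0.7) | 73%, 71% | 49.8, 49.5 | 78%, 80% |

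Repeat runs of 3,000 to 4,000 trials agree to within about three points. Under no true effect and no top-up, type I error was 4.6–4.7% for the t test and 4.4% for the joint model.

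**5. Purely random loss.** Let a fraction d lose T2, unrelated to TH and not replaced. The effective n per arm at T2 with T1 in the model is 25(1 − d)/(1 − dρ²). At d = 0.2 the t test has 20 per arm and 69.5% power for TH (normal approximation).

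| ρ | effective n | TH power | gain in points | BAP power (t test 92.4%) |
|---|---|---|---|---|
| 0.3 | 20.4 | 70.3% | 0.8 | 92.8% |
| 0.5 | 21.1 | 71.7% | 2.2 | 93.6% |
| 0.7 | 22.2 | 73.9% | 4.4 | 94.7% |

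In simulation with 20% random loss the gain for TH was about 0 to 4 points.

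**6. No missing T2.** With d = 0 the effective n is 25, and the day-30 estimate is the same under both methods.

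**The case against.** Several points on the other side stand.

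- An independent-data t test is not confined to one visit. It can be run on a change score or on the mean of T1 and T2, and Statistical Analysis does not rule that out. A reader might infer that the method forces a single visit and that T1 is wasted; the documents do not support that. T1 can enter a T1 comparison. It is unused only for T2, and a summary needing both visits would still drop an infant without T2.
- The harm supposes that day 30 is the comparison of interest, and the documents name no main visit. The fix has to name one.
- A reader might take 64–65% as the power of this plan. That ignores the stated top-up; with it the t test has 71–73%. The bias remains, and so does a gap of about 5 to 9 points to the joint model.
- The loss rule, the correlation and a full effect by T1 are assumptions. The cited text gives no mortality rate, speaks of stopping treatment rather than refusing samples, and does not say that sampling ends at discharge. Discharge would not obviously remove the sicker infants.
- The bias is modest. The standard error with 25 per arm is 64 × √(2/25) = 18.1, so 3.5 to 4.9 units is about 0.2 to 0.3 of a standard error, towards no effect.
- The mixed model does not solve the problem of infants who die before day 30. It treats their T2 as unobserved and in effect predicts it.

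None of this lets the planned test use T1 when T2 is missing, and top-up does not remove selection.

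**Conclusion.** The point holds as a minor one. The plan measures each infant twice after treatment starts, yet provides no way for T1 to inform the T2 comparison when T2 is missing. Under the assumed T1-dependent loss, the T2 t test understates a true TH effect of 50 by about 3 to 5 units. It also has about 5 to 9 points less power than a joint model, with or without top-up. Under random loss of 20% the difference is about 0 to 4 points, and with complete T2 data there is none. BAP has ample power in the random-loss case.

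A reader might go further and infer a risk of false positive results. That would need selective loss to differ between arms for some reason other than a treatment effect. The documents give no ground for expecting it in a double-blind trial, and when the same loss rule applies to both arms the t test keeps its 5% level.

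**What to change.** In Statistical Analysis, specify one mixed model for repeated measures for each marker:

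- outcomes T1 and T2; fixed effects for group, visit and group-by-visit;
- unstructured covariance within infant; REML with small-sample degrees of freedom;
- every randomised infant with T1 or T2 included, also those who were later replaced;
- group difference and 95% CI at each visit, with T2 named as the main contrast;
- the t test kept as a sensitivity analysis;
- deaths before day 30 reported by arm, with a statement that the T2 estimate treats their values as unobserved.

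The cost is wording only: no extra blood, visits or infants, and SPSS, already named, fits the model with its MIXED procedure. The downside is the assumption that T2 loss is explained by arm and T1. That is weaker than what a t test on completers assumes, but the data cannot verify it.
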